Exploratory Aim: In an effort to further understand the complex interaction between study volunteers (interviewing medical students) and study subjects, including how unique interactions between the study representative(s) and the study subjects may affect questionnaire responses and vaccine acceptance decisions, we aim to conduct motivational interviews with 20 vaccine-hesitant participants, and with four study volunteers. Each motivational interview will be conducted by [name], PhD, Associate Professor and Chair of the Department of Communication at Wake Forest University.

We aim to explore the relationship between baseline influenza vaccine hesitancy rates and baseline altruism scores. Effectiveness of our intervention is dependent on parental altruism levels; therefore, we also seek to determine if there is an association between parental altruism and vaccine hesitancy for their children.

Methods and Measures

Setting:

Study subjects will be recruited from two Wake Forest University Baptist Medical Center general pediatric practices: Westgate Pediatrics and Pediatrics - Ford, Simpson, Lively, and Rice. Westgate Pediatrics is located at [name]. Westgate serves a diverse population, with approximately 50% of patients receiving Medicaid services. Pediatrics - Ford, Simpson, Lively, and Rice is located at [name]. This latter practice serves a large population that is generally of a higher socioeconomic status than Westgate Pediatrics, with approximately 25% of patients receiving Medicaid services. Study volunteers will be Wake Forest School of Medicine medical students in their 4th year who volunteer to participate in this project as credit for a 4th year elective rotation.

Design:

A single-arm prospective cohort study will be conducted. The study will enroll as study subjects legal guardians of children who are influenza vaccine-eligible to measure their vaccine hesitancy scores, altruism scores, and the impact of an educational intervention focused on herd immunity on the guardians' vaccine hesitancy score.

Inclusion Criteria:

All legal guardians of children aged 6 months and up who are influenza vaccine-eligible and present to the pediatric clinic.

Exclusion Criteria:

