Legal guardians of children who are not influenza vaccine-eligible including children less than 6 months of age, children on immunosuppressive medications, and children with underlying medical conditions resulting in an immunocompromised state.

Sample Size:

Specific Aim 1: baseline vaccine hesitancy is 25%⁴⁷. Clinically meaningful difference in hesitancy is defined as 15%. This difference can be detected with 80% power with 250 subjects per group.

Specific Aim 2: We anticipate our intervention could reduce vaccine hesitancy from the national baseline of 25% to 15% on the post-intervention survey. Identifying this reduction from 15% to 15% in paired proportions with 80% power requires enrollment of 312 subjects who complete both tests (i.e. enrolling 312 subjects identified as vaccine-hesitant).

Exploratory Aim: Motivational interviews with study subjects (20) and study volunteers (4) will not be powered or statistically analyzed.

Interventions and Interactions

We will conduct a prospective cohort study of families with children aged 6 months and up who are eligible to receive the seasonal influenza vaccine. Subjects who consent to this study will answer questions which will include demographic questions, a baseline 20-item Altruism Scale, and an 8-item Vaccine Hesitancy Scale. The 20-item Altruism Scale will be scored based on a 5-point Likert scale, with each question scoring from 1-5, then added together to give a cumulative score. Higher scores indicate higher altruism. The Vaccine Hesitancy Scale will be scored as previously described: scoring responses for each item will be scored as follows: strongly agree = 1, agree = 2, disagree = 4, and strongly disagree = 5, such that higher values always indicated greater hesitancy. We will then calculate the average score of the 8 items included in the scale, and use the pre-defined average score of ≥ 3 as "hesitant." Subjects identified as vaccine-hesitant based on a Vaccine Hesitancy Score ≥ 3 will be given an educational handout and provided a standardized, brief educational session overviewing the educational handout. At the end of the doctor's visit, subjects will complete a second identical 8-item Vaccine Hesitancy Scale.

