We will also conduct a retrospective chart review of all patients who participated in the initial survey to determine whether the child received the influenza vaccine. Retrospective chart review will also be conducted to estimate the influenza vaccine acceptance rates for each pediatrics practice over the same time period from one year prior.

Two study volunteers will be at each pediatric clinic. A volunteer will approach an eligible parent/guardian in the waiting room prior to their scheduled appointment and obtain informed consent to participate in the study. A consenting subject will complete the Vaccine Hesitancy Scale⁴⁷ orally with the study volunteer. The Vaccine Hesitancy Scale is positive if the average of all questions is greater than or equal to 3. When the study volunteer is inputting and grading the Vaccine Hesitancy Scale in a REDCap survey tool on an iPad, the subject will complete the Self-Report Altruism Scale⁴⁸ and several demographic questions on paper. If the guardian screens positive for vaccine hesitancy (i.e., vaccine hesitancy score average \geq 3), they will be given the informational handout along with a brief script. The parent will have the opportunity to review the intervention in the waiting room and during the visit while the provider is out of the room. If the guardian was deemed vaccine hesitant and was given the intervention, the study volunteer will remain at the nurse's station and wait for the visit to be completed. Once the family is finished, the study volunteer will approach the participant once again and complete the Vaccine Hesitancy Scale orally prior to check out. The subject's child's electronic health record will then be accessed to document whether that patient received the seasonal influenza vaccine that day.

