For Specific Aim 2, our primary outcome will be the change in vaccine hesitancy scores pre- and postintervention, which will be assessed with a paired t-test or Wilcoxon signed-rank test, following review of the score distribution. We will also measure the change in Question #6 (the only Altruism-specific question on the questionnaire) independently, and also compared with each other individual question on the questionnaire, and pre- and post-intervention change will be assessed with a paired t-test or Wilcoxin signranked test, following review of the score distribution. As a secondary outcome, the rate of influenza vaccine uptake will be compared qualitatively to historic controls.

For the Exploratory Aim, we will capture qualitative data and seek trends. No statistical computation will be done on these data.

All data will be entered directly into a Research Electronic Data Capture database and analyzed using SAS v9.4 (Cary, NC).

Human Subjects Protection

Risks for participation are not more than minimal. There is risk of accidental unauthorized release of identifiable personal information. Data access will be limited to study staff. Data and records will be kept locked and secured, with any computer data password protected. Participation in a post-study interview by the study volunteers will not require written consent, but it is voluntary. The grading for the elective course is Pass/Fail, and will be exclusively based on their participation in the actual study, and not the post-study interview, which is voluntary.

Subject Recruitment Methods

All parents who present to either pediatric clinic with children 6 months and up who are eligible for the flu vaccine will be eligible to participate in the study. Two student volunteers will be at each clinic for the recruitment process during flu season (between October and December depending on volunteer schedule availability). A volunteer will approach any parent(s) in the waiting room prior to their schedule appointments to recruit for the study regardless of gender or race/ethnicity.

For the retrospective chart review, there is minimal risk involved to participants. All protected health information will be de-identified prior to data analysis and publications; subject identity will be known only to the study staff. Subjects who participated in the initial arm of the study will be included in the chart review to determine further demographic data and whether the child received the flu vaccine.

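### Aim 2: the score that selects hesitant guardians is also their only 'pre' value, so a significant fall against zero does not by itself show that the handout works

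*Combined protocol and SAP*

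**What the plan says.** - **Design:** "A single-arm prospective cohort study will be conducted".
- **First score:** under Interventions and Interactions, before the visit, "A consenting subject will complete the Vaccine Hesitancy Scale" orally with a study volunteer. This is the only administration before the handout.
- **Selection:** "Subjects identified as vaccine-hesitant based on a Vaccine Hesitancy Score ≥ 3 will be given an educational handout" and a short standardised session.
- **Second score:** only the selected are followed. "If the guardian was deemed vaccine hesitant and was given the intervention, the study volunteer will remain" until the visit ends; then "the study volunteer will approach the participant once again and complete the Vaccine Hesitancy Scale orally prior to check out". The instrument is unchanged: "subjects will complete a second identical 8-item Vaccine Hesitancy Scale".
- **Analysis:** for this aim the Analytical Plan states "our primary outcome will be the change in vaccine hesitancy scores pre- and postintervention, which will be assessed with a paired t-test"; the alternative, depending on the score distribution, is a Wilcoxon signed-rank test. Question 6 is tested the same way, alone and against each other item.
- **Purpose and size:** Objectives words Aim 2 as an assessment of the intervention's effectiveness. Sample Size asks for 312 hesitant guardians with both scores.

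The plan has no second baseline, no untreated hesitant group and no retest of non-hesitant guardians, and it does not mention regression to the mean. Historic controls are used only for vaccine uptake, as a qualitative secondary comparison, so they do not bear on the score outcome.

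**The concern.** A first score contains some momentary error. Guardians chosen because that score was high include a surplus whose error ran upwards. On a second administration the error is drawn afresh and the group mean drops, even if the handout does nothing. Both planned tests take zero change as the null, so they test the wrong value for a group selected in this way.

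This is the primary outcome of the interventional aim. The only significance threshold in the document, p < 0.05, stands in the Aim 1 paragraph, and no minimum meaningful score change is given. A significant fall could therefore come from the selection rule alone and still be read as effectiveness. The Question 6 change taken alone has the same fault.

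**Working it through.** **Inputs from the documents.** 312 pairs (Sample Size, Specific Aim 2); "baseline vaccine hesitancy is 25" per cent (Sample Size, Specific Aim 1), used as the fraction selected; threshold 0.05, taken as two-sided, so 2.5% in the favourable direction.

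**Assumptions.** Normal scores with SD 1 at both administrations, no handout effect, and retest correlation r. The documents give no r, so a range is shown.

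**The plan's 312.** A McNemar sample size with 25% and 15% entered as the two discordant cells (sum 0.40, difference d = 0.10), two-sided 0.05 and 80% power:

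[1.960 × √0.40 + 0.842 × √(0.40 − 0.10²)]² / 0.10² = 311.6, so 312.

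The figure reproduces on that reading. It is used below only as the number of pairs.

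**Step 1, mean and variance of the selected.** The top 25% lie above c = 0.6745. Their mean is φ(c)/0.25 = 0.3178/0.25 = 1.271 SD. Their variance is 1 − 1.271 × (1.271 − 0.6745) ≈ 0.242.

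**Step 2, expected fall with no effect.** Fall = (1 − r) × 1.271.

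**Step 3, SD of the change.** √[(1 − r)² × 0.242 + 1 − r²].

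**Step 4, chance of a significant fall.** Noncentral t with 311 degrees of freedom and noncentrality fall/(SD/√312). At r = 0.90 the fall is 0.127, the SD is √(0.01 × 0.242 + 0.19) = 0.439, and the noncentrality is 0.127/(0.439/17.66) = 5.1.

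| r | Spurious fall (SD) | Chance of a significant fall, 312 pairs |
|---|---|---|
| 0.80 | 0.25 | about 100% |
| 0.90 | 0.13 | 99.9% |
| 0.95 | 0.06 | 95% |
| 0.98 | 0.03 | 61% |
| 0.99 | 0.01 | 35% |
| 0.995 | 0.006 | 20% |
| 0.998 | 0.003 | 10.5% |

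The chance exceeds 50% unless r is above about 0.985.

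**Sensitivity.** For r = 0.80, 0.90, 0.95, 0.98, 0.99:
- 15% selected: 100%, 100%, 99%, 78%, 49%.
- 35% selected: 100%, 99%, 84%, 46%, 26%.
- 125 pairs (assumed: 25% of two Aim 1 groups of 250): 99.6%, 90%, 61%, 29%, 17%.

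**Signed-rank test.** Simulation under the same model gives 99.9%, 93% and 59% at r = 0.90, 0.95 and 0.98, so the alternative test does not avoid the problem.

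**The plan's own scoring.** Simulating eight items scored 1/2/4/5 with 25% hesitant, 312 pairs and no effect, whole-scale r of 0.984, 0.968, 0.943 and 0.912 gave a significant fall in 53%, 83%, 97% and 99.8% of trials. The falls were 0.02, 0.05, 0.08 and 0.11 points. Question 6 alone fell significantly in 11%, 18%, 28% and 41%.

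**Question 6 against the mean of the other items.** If all items carry the same noise, the contrast falsely favours Question 6 in 2.3% to 3.6% of null trials, close to nominal. Equal reliability is not sufficient, because an item's regression-to-the-mean fall follows its error variance in points. With equal reliability but a Question 6 SD 1.5 or 2 times that of the other items, simulation gave about 14% and 30% false favourable results.

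**The case against.** **The retest correlation may be very high.** The scale is identical, oral, and repeated within one visit, so recall could push r close to 1. This stands: nobody can say from the documents which row of the table applies. But the rate is still four times nominal at r = 0.998 (10.5/2.5), and the plan offers no r to rely on.

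**The bias is small.** Also true. It is 0.06 SD at r = 0.95. A fall of 0.50 SD would need r of about 1 − 0.50/1.271 = 0.61 to arise from selection alone.

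**It is a single-arm pilot and says so.** That is a legitimate design, and the plan nowhere says that p < 0.05 alone establishes effectiveness. What remains is that Aim 2 is worded as effectiveness and nothing qualifies how a significant fall will be read.

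**Stronger readings that the documents do not support.** A reader might infer that a false positive is near certain. That depends on an r that is not given. A reader might infer that any fall will be an artefact, or that the handout does not work. Neither follows, since the bias is bounded and small at high r.

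A reader might also infer that a calculated correction could restore a valid test, for example by finding the smallest r at which the fall still exceeds expectation, r* = 1 − L/G (L and G are defined under the fix). It cannot be relied on for that. In null simulations r* fell below the true r in about 3% of trials when noise was even across the scale, but in 84% (r = 0.94) and 62% (r = 0.82) when noise was concentrated near the cut-off. With a right-skewed true score it erred the other way (0.1% to 0.3%). Those shapes are assumptions, but the 1/2/4/5 scoring has no midpoint, so a wavering guardian jumps two points and uneven noise is plausible.

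**Conclusion.** The concern holds, and it is about interpretation. Selection and baseline use the same single score, only the selected are retested, and there is no comparator for the score outcome. With an inert handout the expected change is therefore a fall, and p < 0.05 against zero does not by itself show effectiveness.

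Under normal scores, 25% selected and 312 pairs, the false-positive chance runs from about 100% at r = 0.80 to about 10% at r = 0.998. The existence of the bias needs only r below 1; its size rests on those assumptions. A small significant fall could be wholly spurious. A large one could not be put down to this bias, though the visit itself and repeated oral interviewing would remain as rival explanations. Because this is the primary outcome and the remedy is cheap, the plan should be changed.

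**What to change.** Required, in Analytical Plan, Specific Aim 2; wording and reporting only:

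1. Keep the planned test. State that p < 0.05 against zero is not evidence of effectiveness. Describe the result as an uncontrolled pre-post change for which regression to the mean, the visit itself and repeated oral interviewing are rival explanations.
2. Report the mean fall with its 95% CI beside an illustrative regression-to-the-mean fall, (1 − r) × G, over a range of r such as 0.80 to 0.995. G is the baseline mean of the retested hesitant cohort minus the baseline mean of all surveyed guardians; both are already collected. State that this assumes a straight-line regression of second on first score with even noise across the scale, and that it can understate the expected fall if noise is concentrated near the cut-off. With L the lower 95% limit of the mean fall, r* = 1 − L/G may be shown as a sensitivity figure under the same assumption, not as a significance test or a calibrated limit.
3. Report the Question 6 change alone as descriptive. Treat its contrasts with the other items as supportive only. State that they remove regression to the mean only if the items have equal error variance in points, and that equal reliability is not enough.

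Optional, and the only part needing new data: repeat the eight items at check-out in some non-hesitant guardians. Use the regression slope of second on first score to inform r. The ordinary correlation in that group is range-restricted: a true 0.90 would appear as about 0.83, and 0.95 as about 0.91. Precision is modest. With 100 such guardians the slope is known to within 1.96 × √[(1 − r²)/(0.535 × 100)], about 0.12 at r = 0.90 and 0.08 at r = 0.95, where 0.535 is the variance of normal scores in the lower 75%.

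**Cost.** A weaker conclusion, a little more analysis, and no single pass-or-fail rule for effectiveness. The required changes leave the planned test, its power and all procedures as they are.

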Promoting Altruism to Enhance Vaccine Acceptance NCT04568590 Study Protocol and Statistical Analysis Plan Document Date: 6/27/22

Cohort Study to Determine the Effect of an Educational Intervention Focusing on Herd Immunity to Enhance Vaccination Uptake Rates

Principal Investigator(s), Resident Investigator:

[name], MS, Co-Principal Investigator [name], Co-Principal Investigator [name], DO, Resident Investigator

Sponsor or Funding Source: Center for Vaccines at the Extremes of Aging Pilot Funds

Background, Rationale, and Context

Vaccine hesitancy is on the rise in the United States, which is causing a resurgence of vaccine-preventable diseases. Vaccine hesitancy regarding the seasonal influenza vaccine is especially prevalent, with a recent study indicating hesitancy prevalence of 6.1% for routine childhood vaccines but 25.8% for influenza vaccine¹⁻⁶. This trend is particularly concerning today as the world awaits a COVID-19 vaccine, the effectiveness of which will be critically threatened by poor uptake due to vaccine hesitancy. Uniform strategies to address vaccine hesitancy have met challenges due to pervasive online misinformation, and the heterogeneity of the vaccine-hesitant community, which crosses racial, socioeconomic, educational, and political lines^{3, 7-26}. However, a common thread that globally may contribute to vaccine hesitancy is rising individualism, the moral stance that the individual takes precedence over a larger social group²⁷⁻²⁹. Altruistic, prosocial motivation seems to be an essential component of vaccine acceptance³⁰. Altruism has also been identified as the major motivator in subjects willing to participate in preventative vaccine trials³¹. One potential strategy to increase altruism amongst vaccine hesitant individuals is to provide education on the concept of herd immunity. A recent scenario study found that explicitly communicating the role of herd immunity increased people's intention to accept vaccines, especially in Western, individualist cultures³². Strategies like this to promote altruism in order to enhance vaccine uptake could improve public health outcomes. How to best communicate the benefits of herd immunity in an increasingly individualistic, nationalistic climate is unclear but must be addressed.

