Pediatric oncology patients represent a potentially excellent population on whom to base a herd immunity educational effort aimed at enhancing altruism in vaccine-hesitant parents: pediatric cancer patients tend to elicit strong sympathetic responses from the public; they come from all communities in the US and are therefore local; and they rely on herd immunity for protection from vaccine-preventable infections because they are largely unable to receive vaccines due to their immunocompromised state³³⁻⁴⁶. Therefore, we hypothesize that a brief educational encounter on herd immunity focusing on local pediatric cancer patients' risk and sponsored by local pediatric oncology providers will increase altruism scores and directly correlate with an increase in seasonal influenza vaccine acceptance. We aim to explore the overall effectiveness of this educational intervention, and also aim to explore whether there may be an identifiable subpopulation most amenable to this type of intervention based on baseline altruism score, race, educational level, or political affiliation.

Objectives

Specific Aim 1: To identify associations with influenza vaccine hesitancy, including parental demographics and altruism score, in families with healthy children attending two pediatric practices.

Specific Aim 2: In the cohort of families with baseline vaccine hesitancy, to assess the effectiveness of a pilot educational intervention focusing on the development of herd immunity for pediatric oncology patients by measuring:

- a. The change in vaccine hesitancy scores pre- and post-intervention.
- b. The change in the score of question number 6 on the Vaccine Hesitancy Scale, which uniquely and specifically relates to altruism. We will also compare the change in this individual score

with the change in the other individual question scores, which relate to other realms of vaccine confidence, including safety, efficacy, and trust.

c. The rate of influenza vaccine uptake compared to historic controls from previous influenza seasons.

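### Vaccine uptake is to be compared only qualitatively with historic controls: no difference and no interval are planned, and the historic rate covers whole practices rather than hesitant families

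*Combined protocol and SAP*

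**What the plan says.** The title gives the purpose as to "Enhance Vaccination Uptake Rates". Under Objectives, Specific Aim 2 is set "In the cohort of families with baseline vaccine hesitancy, to assess the effectiveness of a pilot educational intervention", and item c is "The rate of influenza vaccine uptake compared to historic controls from previous influenza seasons".

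The Analytical Plan gives uptake one sentence, as a secondary outcome: "the rate of influenza vaccine uptake will be compared qualitatively to historic controls". In the same paragraph, "our primary outcome will be the change in vaccine hesitancy scores pre- and postintervention", and that outcome has a named test (paired t-test or Wilcoxon signed-rank).

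Interventions and Interactions describes the data. Charts are reviewed for everyone who took the initial survey, to see whether the child was vaccinated. For those who complete the visit procedures, the record is checked for vaccination on that day. A separate chart review will "estimate the influenza vaccine acceptance rates for each pediatrics practice over the same time period from one year prior". No restriction to hesitant families is stated for that historic group, and neither its size nor its rates are given.

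Setting puts the Medicaid share at about 50% at Westgate and describes the other practice as "generally of a higher socioeconomic status than Westgate Pediatrics, with approximately 25% of patients receiving Medicaid services". Practice is modelled (as a random effect) for Aim 1 only. Nothing is said about how practice enters the uptake comparison.

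**The concern.** Uptake is the study's only behavioural outcome, and readers will look for it first. A comparison by eye lets the report say that uptake rose, or did not rise, without showing how far chance alone could move the figure.

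Two further features make a by-eye reading hazardous:

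- **Who is compared.** Subjects who receive the intervention are selected for hesitancy. The historic patients, as described, are not. The two rates would differ with no intervention at all.
- **How practices are combined.** The practices differ in case mix. If they were pooled, and the study's split between them differed from the historic split, the pooled rates would differ for that reason too. The plan does not say whether it will pool.

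The definitions also need reconciling. The objective speaks of several previous seasons and the chart review of one year prior. Subjects have a same-day vaccination check, while historic acceptance is not defined.

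**Working it through.** **The plan's own figures.** No sample size or precision is stated for uptake. The Aim 2 size of 312 is for paired hesitancy proportions. It reproduces from the McNemar formula (two-sided 0.05, 80% power, difference d = 0.10) if 25% and 15% are taken as the two discordant cells, so ψ = 0.40:

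N = [1.96√0.40 + 0.8416√(0.40 − 0.01)]² / 0.10² = 311.6, rounded up to 312.

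I use 312 below only as the planned number of hesitant subjects. Uptake rates and historic numbers are not in the documents, so those inputs are assumed and varied.

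**1. Chance variation in study uptake.** Half-width = 1.96√[p(1 − p)/312].

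| p | Half-width (points) |
|---|---|
| 30% | 5.1 |
| 40% | 5.4 |
| 50% | 5.5 |

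**2. Chance variation in a difference from the historic rate.** Half-width = 1.96√[p(1 − p)(1/n + 1/m)], with n study subjects, m historic patients and p from 20% to 70% in both periods.

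| n | m | Half-width (points) |
|---|---|---|
| 312 | 312 | 6.3 to 7.8 |
| 312 | 1000 | 5.1 to 6.4 |
| 312 | 5000 | 4.6 to 5.7 |
| 125 | 312 to 5000 | 7.1 to 10.4 |

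The last row shows what follows if only the Aim 1 total of 2 × 250 = 500 is surveyed and 25% are hesitant. Intervals within a single practice would be wider than these.

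**3. Hesitant subjects against a whole-practice rate.** Suppose a share of 25% is hesitant (the plan's baseline), with uptake h in hesitant families and u in the others. The practice rate is 0.25h + 0.75u, so with no intervention effect

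hesitant rate − practice rate = 0.75(h − u).

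| h (assumed) | u (assumed) | Practice rate | Gap (points) |
|---|---|---|---|
| 10% | 60% | 47.5% | −37.5 |
| 20% | 60% | 50% | −30 |
| 30% | 70% | 60% | −30 |
| 40% | 60% | 55% | −15 |

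The gap exceeds the chance half-widths in step 2 in every scenario, and comparing within practice does not remove it.

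**4. Practice mix, only if the practices are pooled.** Shift = (difference in practice share) × (gap between practice rates). For assumed share differences of 10 to 40 points and rate gaps of 5 to 25 points, this runs from 0.10 × 5 = 0.5 to 0.40 × 25 = 10 points. Within a practice it is zero.

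**5. The closest like-for-like comparison: all surveyed subjects.** Finding 312 hesitant subjects at 25% hesitancy means surveying 312/0.25 = 1,248. With n = 1,248, m from 1,248 to 5,000 and p from 20% to 50%, the step 2 formula gives ±2.5 to 3.9 points. An assumed 10-point rise confined to hesitant families would appear as 0.25 × 10 = 2.5 points. The comparison is fairer, but it may well be inconclusive.

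**The case against.** The strongest defence is that uptake is a declared secondary outcome of a single-arm pilot, that the Aim 2 primary outcome has a proper test, and that a qualitative comparison is honest caution with controls this weak. It can be added that an interval on hesitant uptake minus the practice rate would do harm. With a built-in gap of 15 points or more and a half-width of about 5 to 8, it would probably exclude zero and suggest that uptake fell when nothing had changed.

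Much of this stands. It limits the severity, and it rules out the simplest remedy of putting an interval on that difference and treating it as the result. It does not justify leaving out uncertainty altogether: caution can be stated in the label, and a bare pair of rates invites the same misreading.

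Two stronger readings are tempting but unsupported:

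- A reader might infer that uptake will go unestimated. The plan obtains a rate in subjects and in each practice; what it lacks is the estimated difference and its uncertainty.
- A reader might infer that practice mix will distort the result. No section says the practices are pooled, historic rates are planned by practice, and neither the enrolment split nor uptake by practice is given. Medicaid shares alone do not establish a bias.

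**Conclusion.** The concern holds in limited form, as a change that should be made to a secondary analysis. Uptake is compared with no estimated difference and no interval, although the data for both are already to be collected. Chance alone accounts for about ±5.1 to 5.5 points on the hesitant subjects' uptake (rates of 30% to 50%) and about ±4.6 to 7.8 points on a difference (rates of 20% to 70%, historic numbers of 312 to 5,000). Both rest on reaching 312 hesitant subjects.

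The larger problem is the comparator. Hesitant subjects set against whole-practice rates would be expected to show lower uptake with no change, by 15 to 37.5 points in the scenarios tried. The direction is what one expects of hesitant families; the size rests wholly on assumed rates. Practice mix is a conditional addition, and the documents do not allow its size to be fixed. None of this affects the score-change outcome.

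**What to change.** Replace the qualitative comparison in the Analytical Plan with two reports:

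1. **Hesitant subjects.** Give uptake by practice with a 95% interval, beside that practice's historic rate. State that the historic rate is not limited to hesitant families and that the gap is not an intervention effect.
2. **All surveyed subjects.** Give uptake minus the historic rate within each practice, and combined using the study's practice mix, each with a 95% interval. For practice k with weight w_k = n_k/n, the combined difference is Σ w_k(p_k − q_k), with variance Σ w_k²[p_k(1 − p_k)/n_k + q_k(1 − q_k)/m_k]. Here p and n are the study rate and number, and q and m the historic ones.

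Use one definition of uptake in both periods, and reconcile the number of historic seasons between Objectives and Interventions and Interactions. Label both reports non-randomised and give no p-value.

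The cost is a few sentences and a little more analysis on charts already to be reviewed. There are two real downsides: the intervals may show that the uptake result is inconclusive, and the all-subjects comparison dilutes any effect confined to hesitant families.
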